2 RATIONALE

Mental disorders are estimated to account for around 5% of A&E attendances in the UK and almost 30% of acute inpatient bed occupancy and acute readmissions.^{2, 4, 5} The experience of people attending A&E for a mental health problem remains less than satisfactory, with frequent delays in receiving appropriate care (breaches), a lack of provision of recommended interventions and poor continuity of care.^{4, 13, 14} There is consistent evidence that particular black and minority ethnic communities are over-represented in the coercive and custodial aspects of mental health crisis care, particularly those who experience high levels of poverty.¹⁵ Although the emergence of liaison psychiatry services has enabled organisations to provide responsive mental health advice and assessment within emergency care settings, there remain wide variations in service provision¹⁶ and ongoing challenges to sustainability¹⁷ with little ability to undertake in-depth assessments in a more settled environment outside of statutory waiting time standards. The introduction of crisis resolution

and home treatment (CRHT) teams and triage wards has offered little benefit in reducing contact with acute services, inpatient admissions or costs across the wider in-patient system compared with standard models of care,¹⁸⁻²⁰ with ongoing staff concerns over the negative impact on the accuracy of triage decisions for mental health presentations,^{21, 22} while inpatient care remains unpopular, expensive and sometimes detrimental for individuals and their families.^{2, 7, 23, 24}

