• Examine the referral pathways into MHDUs and the care pathways followed by people before and following an admission to the participating MHDUs, and the extent to which these are influenced by organisational pressures and service users' socio-demographic characteristics and psychiatric history, using electronic patient record (EPR).

Outcomes

• A comprehensive profile of those individuals visiting the MHDU which includes descriptions of the care pathways before and following an admission to the MHDU.

• A model of individual-based factors most relevant to change in key MHDU service user outcomes (e.g., decrease in number of A&E presentations from the period pre-MHDU admission to the period post-MHDU discharge).

Design and Methods

ITS analyses will allow us to assess whether the introduction of MHDUs for people experiencing a mental health crisis accessing emergency care has affected service delivery outcome measures. Service re-design also needs to be examined from a broader context to better understand who is referred to MHDUs (including an equalities 'impact assessment') and what works for which groups of service users and why. A prospective, longitudinal study will address the following research questions:

- 1) How does attending an MHDU impact on psychiatric inpatient admissions and A&E psychiatric episodes/breaches for current MDHU users?
- 2) What are the care pathways before and following an admission to the MHDU for current MDHU users?
- 3) What is the impact of the introduction of MHDUs on inequalities of access to acute mental health services?

Participant selection criteria

All service users at south west London, Lincolnshire, Birmingham, and Sheffield MHDU sites referred for the first time to a MHDU over a 9-month period will be eligible to participate (there are no eligibility criteria other than first admission to MDHU and capacity to consent to participate in research). For sites where service use data cannot be extracted anonymously (e.g. Lincolnshire), only those service users who consent to participation will be included.

Data collection

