Baseline data will be collected for all included participants on socio-demographics (e.g., age, gender, ethnicity, sexuality, postcode) and known predictors of psychiatric admission and health care utilisation by UK adults with mental illness (e.g. diagnosis, previous inpatient admissions, accommodation status, comorbidity, high previous health care utilisation).^{56, 57} In line with previous research, discharge destination after MHDU assessment being admission to psychiatric hospital will be used as a 'proxy of severity' of presentation.⁵⁸ Fields will be specified in pseudonymised Clinical Record Interactive Search (CRIS) reports for those sites with the CRIS facility (SWLSTG and Birmingham), and as appropriate to local Electronic Patient Records system through working with Information Management teams at other sites. The quality and completeness of EPR data is critical to the study. Although data resources including EPR are not shaped by research priorities,⁵⁹ the positive predictive value of EPR has previously been reported as high.⁶⁰ We will test data requirements and identification of fields through repeat iterations as necessary at each site prior to WP3 commencing.

Individual mental health service use data (including those outcomes specified in WP2 in addition to total number of admissions and use of community mental health team (CMHT) and other mental health trust services), numbers of A&E presentations (measured as psychiatric liaison episodes in A&E as recorded in the EPR) and transfers by ambulance and police to MDHU will be collected for each participant for 9 months prior to MHDU admission and 9 months post-discharge. The primary outcome for Mental Health Trust will be the number of informal admissions, and for the acute Trust will be number of A&E presentations.

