Multivariate regression models will be constructed for primary and secondary outcome measures to explore the impact of each predictor variable. It has been proposed that for (multivariate) logistic regression, the minimum number of cases to include is n = 10 k / p, where p is the smallest of the proportions of negative or positive cases in the population and k the number of independent variables.⁶³ For example, if there are (up to) 5 explanatory variables to include in the model and the proportion of positive cases (for key outcomes) in the population is 0.20 (20%), the minimum number of cases required is N=10 x 5 / 0.20 = 250. Throughput for all MHDUs in the study is approximately 30-40 service users per month. We assume informed consent will be obtained for 50% of service users referred to MHDUs in Lincoln and Sheffield, yielding (Lincolnshire = 138; Sheffield = 75). We plan to obtain anonymised data for patients in Birmingham and SWLSTG, (SWLSTG = 270 Birmingham = 668). Participant consent is not required for collection of anonymised data. Including both types of data (collected anonymised data and from consented participants), the anticipated sample size is 1151. These sample sizes will be adjusted in discussion with study sites in relation to actual rates of admission.

Analytical strategy

Initially, the sample of MHDU service user participants will be described with respect to sociodemographics and relevant factors associated with psychiatric admission and health care utilisation (e.g. ethnicity, diagnosis, previous inpatient admissions, accommodation status, comorbidity, previous

health care utilisation).^{56, 57} Where appropriate, individual mental health service use data will be compared between the pre- to post-MHDU discharge periods using paired sample t-tests or McNemar mid-*p* test for binary matched-pair data⁶⁴ depending on distributional properties. Where continuous variables do not meet requirements for univariate normality using skewness and kurtosis estimates, bootstrapping using 2000 replications⁶⁵ will be employed to calculate 95% confidence intervals of mean difference and associated p values.

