We will use Generalized Linear Modelling (GLM) to develop Logistic and Poisson regression models which examine relationships between important service/service user characteristics and (individual) mental health service use data post discharge from the MHDU. For example, Poisson regression will be employed to estimate relative risks (RRs) and 95% confidence intervals (CIs) for the associations of independent variables (ethnicity, diagnosis, previous inpatient admissions, accommodation status, comorbidity, previous health care utilisation, time spent in MHDU, severity of presentation as indicated by discharge destination after MHDU assessment)⁵⁸ with those outcome measures that use count data (e.g., total number of admissions and numbers of A&E presentations in the 9 months after MHDU discharge). We will also develop regression models using GLM (e.g., Linear and/or Logistic, depending on data distribution) to explore which independent variables are most closely related to change in primary outcome variables (e.g., decrease in number of A&E presentations from the period pre-MHDU admission to the period post-MHDU discharge). For all categorical independent variables in models (e.g., diagnosis), the reference group will be selected on the basis of it being 1) the largest or 2) most interpretable.⁵⁶ To account for missing data on relevant variables (e.g., accommodation status), a multiple imputation approach will be adopted to create imputed datasets using chained equations.⁶⁶ We will check for the occurrence of multicollinearity and calculate Cook's distances⁶⁷ to identify influential outliers. We will use two-sided significance tests for all analyses with statistical significance set at a p value of 0.05.

WP5.Qualitative longitudinal study (months 7-21)

Objective

• To examine qualitative interview data to understand experiences before, during, and after referral to MHDU from the perspective of service users and carers, and the decision-making process of A&E, crisis services and MHDU staff along the crisis care pathway.

Outcomes

- A detailed understanding of MHDU service user and carer experience including pathways before and after MHDU admission.
- A detailed understanding of staff experience of MHDU implementation, particularly that concerning decisions made about MHDU referral/admissions, assessments and onward signposting.

Design and Methods

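### WP4 regression lists time in the MHDU and discharge destination beside ethnicity, diagnosis and history; entered together, the relative risks for person characteristics exclude any influence acting through the unit's decisions

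*Protocol*

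**What the plan says.** All places are in Protocol section 5, WP4, unless stated.

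- **Objective.** WP4 examines referral pathways into the MHDU and care pathways before and after it, and how far these are influenced by organisational pressures and by service users' socio-demographic characteristics and psychiatric history.
- **Data collection.** In the paragraph on baseline data, "discharge destination after MHDU assessment being admission to psychiatric hospital will be used as a" proxy for severity of presentation.
- **Sample size.** "Multivariate regression models will be constructed for primary and secondary outcome measures to explore the impact of each predictor variable".
- **Analytical strategy.** Poisson regression is given as an example. The listed independent variables begin "ethnicity, diagnosis, previous inpatient admissions, accommodation status, comorbidity, previous health care utilisation, time spent in MHDU", and the last two are "time spent in MHDU, severity of presentation as indicated by discharge destination after MHDU assessment". The outcomes include "total number of admissions and numbers of A&E presentations in the 9 months after MHDU discharge". A multicollinearity check is planned. No model without the two post-admission terms is described, and neither term is identified as an intermediate step.
- **Section 6, Study Setting.** The MHDU's function is assessment and therapeutic input, followed by admission, discharge or signposting onward. Destination is therefore the result of the unit's work.

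**The concern.** Ethnicity, diagnosis, previous admissions, accommodation, comorbidity and previous use are settled before the person enters the unit. Time in the unit and discharge destination are not. They follow from the unit's assessment and are the first steps of the pathway that the objective wants explained.

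A regression holding both kinds of variable answers a narrower question than the objective asks. It compares people with different characteristics who stayed equally long and were sent to the same destination. If a characteristic changes the chance of onward admission, and onward admission changes later use, that route is held fixed and drops out of the relative risk.

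There is a second mechanism. If severity that the record does not capture drives both destination and later use, people with the same destination but different characteristics will tend to differ in severity. Conditioning on destination then creates an association that was not there before.

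What is at stake is interpretation. A ratio near 1 for ethnicity or diagnosis could be reported as no influence on the later pathway, when it only shows none beyond the unit's own decisions.

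**Working it through.** **The plan's own figures.** The only calculated figures for these models are sample sizes, and both reproduce: 10 × 5 / 0.20 = 250, and 138 + 75 + 270 + 668 = 1,151. The point concerns which variables enter the model and disputes neither figure.

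**Why joint entry is the likelier reading.** The sample size text calls the models multivariate and says they explore the impact of each predictor. A multicollinearity check matters only when predictors are fitted together. This is inference: the list follows the words 'For example', and no sentence says that all terms enter one model.

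**Inputs for size.** The protocol gives no effect sizes, so these are assumptions shown as a range. Onward admission is 30% in one group and 38% or 44% in the other. People admitted onward have R = 1.5, 2 or 3 times the later use. The characteristic has no direct effect.

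**Route through destination only.** The mean count in a group with onward admission probability p is proportional to 1 + p(R − 1). The total ratio is [1 + p₁(R − 1)] / [1 + p₀(R − 1)].

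| Onward admission | R = 1.5 | R = 2 | R = 3 |
|---|---|---|---|
| 44% v 30% | 1.22/1.15 = 1.061 | 1.44/1.30 = 1.108 | 1.88/1.60 = 1.175 |
| 38% v 30% | 1.19/1.15 = 1.035 | 1.38/1.30 = 1.062 | 1.76/1.60 = 1.100 |

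Within a destination the two groups have the same mean, so the ratio adjusted for destination is 1.00 in all six cells.

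**With unrecorded severity acting on destination and later use.** In simulated cohorts of 400,000 with these values, the adjusted ratio was about 0.95 (44% v 30%) and about 0.97 (38% v 30%).

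**A second set of assumed values.** Here 30% of people have the characteristic, the reference log-odds of onward admission correspond to 20%, the characteristic multiplies those odds by 1, 2 or 3, and each cohort has 400,000 people.

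| Scenario | Without destination | With destination |
|---|---|---|
| Odds ratio 2, R = 1.5, no shared cause | 1.06 | 1.00 |
| Odds ratio 2, R = 2, no shared cause | 1.12 | 1.00 |
| Odds ratio 3, R = 3, no shared cause | 1.32 | 0.99 |
| Odds ratio 2, R = 1.5, shared severity | 1.06 | 0.95 |
| Odds ratio 2, R = 1.5, stronger shared severity | 1.06 | 0.89 |
| Odds ratio 2, R = 1 (destination has no effect on use), shared severity | 1.00 | 0.95 |
| Odds ratio 2, R = 1.5, shared severity, plus direct ratio 1.2 | 1.27 | 1.14 |
| Characteristic does not affect destination, direct ratio 1.3 | 1.30 | 1.30 |

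The R = 1 row isolates the second mechanism: there is nothing to remove, yet adjustment gives 0.95. In the direct-effect row, most of the association survives. In the last row there is no distortion.

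**Precision at the planned size.** Take 1,151 people, 25% with the characteristic, a baseline mean of exp(−0.5) = 0.607 and Poisson variance only. For 44% v 30% and R = 1.5, the expected events are 863 × 0.607 × 1.15 ≈ 602 and 288 × 0.607 × 1.22 ≈ 213. The standard error is √(1/602 + 1/213) = 0.080, so the 95% interval around 1.06 is about 0.91 to 1.24. The same steps give about 0.96 to 1.28 around 1.11, and 1.03 to 1.34 around 1.18.

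**Not calculated.** Time in the MHDU was not simulated. The same reasoning applies because it too is determined after admission, but no size is claimed for it.

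**The case against.** **The protocol does not fix one joint model.** It speaks of models in the plural, introduces the list as an example, and sizes its logistic illustration on up to five explanatory variables when eight are listed. The final covariate sets may be settled in an analysis plan that is not at hand. This stands, and the point is conditional on joint entry.

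**The language is largely associational, and both terms have a purpose.** Time in the MHDU is a service characteristic, and Table 1 gives an extended stay with no effect on later outcomes as an example WP4 finding. Destination is the only severity measure listed, so a model without it leaves person characteristics confounded by presenting severity. This also stands. It argues against deleting the terms or resting conclusions on the first model alone. It does not argue against showing both, because the objective speaks of influence and the sample size text of impact.

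**Stronger readings to avoid.** A reader might infer that ethnic differences would be reported as absent or reversed. The documents do not support that. Direct effects survive, and reversal needs a common cause outside the model, which is plausible but not established. Nor can one infer that WP4's inequality question would be answered wrongly. The Rationale notes that "particular black and minority ethnic communities are over-represented in the coercive and custodial aspects of mental health crisis care", but that is background. The WP4 question concerns access to acute services, whereas this regression concerns use after MHDU discharge. Care pathways are also described separately in WP4, and discharge decisions are explored in WP5.

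**Power is limited.** Two of the three intervals computed for 44% v 30% include 1, so the first model would often not show a difference of this size either. That limits what either model can conclude. It does not make the two estimates interchangeable.

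**Conclusion.** The point holds in a limited form. The listed covariates mix characteristics fixed at entry with two variables determined by the unit afterwards, one of them labelled as baseline severity. If fitted jointly, the relative risks for person characteristics are conditional on the unit's decisions and do not measure total influence on the later pathway.

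Under the first set of assumptions, the part lost is a total ratio of about 1.04 to 1.18 falling to about 1.00, or slightly below 1 with shared unrecorded severity. The wider values in the second set give up to 1.32 falling to 0.99, and as low as 0.89 with stronger shared severity. Every effect size is assumed, only destination was quantified, and the loss is confined to influence that runs through destination or stay.

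This is an inexpensive improvement to reporting and interpretation. It does not touch the WP2 and WP3 effect estimates.

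**What to change.** In the WP4 analytical strategy:

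1. Report associations of person characteristics first from a model holding only variables fixed at MHDU admission: socio-demographics, diagnosis, previous admissions, previous use, accommodation and comorbidity.
2. Report them again from a second, labelled model that adds time in the MHDU and discharge destination.
3. Show both sets of relative risks side by side. Describe the second as conditional on the unit's decisions, and state that a null there is not read as absence of influence.
4. In the data collection text, note that destination is recorded after assessment and is not a baseline variable.

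**Cost.** One extra model and one table column, from data already planned. The first model is not adjusted for presenting severity, so neither model should carry the conclusion alone.

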6 STUDY SETTING

This study takes place in Mental Health Decision Units (MHDUs; sometimes called Psychiatric Decision Units, or Crisis Assessment Units). There is no single service specification for MHDUs but rather a shared set of characteristics that distinguish units from other hospital based assessment services such as Triage Wards. Triage or Assessment wards are hospital wards 'to which all patients requiring admission will go for initial assessment and treatment. Length of stay is anticipated to be brief and patients will either be discharged or transferred to a treatment ward if requiring a longer period of admission'.⁹ MHDUs, in contrast, receive targeted referrals of people in acute mental health crisis, prior to a decision about admission being made, for purposes of assessment, therapeutic input, and either subsequent admission, discharge or forward signposting to appropriate recovery and preventative services. MHDUs offer an alternative pathway - to acute admission - for people who experience excessive stays in emergency departments, frequent use of other services, such as the police and ambulance services, and who have complex and frequent crisis-related needs. Generally, all admissions to MHDUs are voluntary - whereas Triage Wards will admit people under assessment or treatment sections of the Mental Health Act - although some MHDUs make a limited number of specific exceptions to this (e.g. step-down from Section 136 Suite). MHDUs are configured as an integrated element of the crisis care pathway alongside CRHT teams and psychiatric liaison teams, and, where provided, street triage and crisis houses, and aim to reduce admission to standard acute care - especially avoidable short admissions and expensive out of area or private admissions - as well as subsequent crisis presentations at A&E. Furthermore, as admission to MDHU is not a formal inpatient admission, MDHU staff are not required to complete inpatient treatment plans or the clustering tool for admission as they would on a triage ward, the focus of assessment and planning in the MDHU being on community-based provision in the medium term rather than inpatient care.

Referrals to MHDU can be made from a range of services including liaison psychiatry teams (typically from A&E departments), Crisis Resolution & Home Treatment teams and street triage teams, with referrals triaged at a decision point prior to admission to the MHDU. MHDUs do not accept self- or family referrals, except, by implication, via A&E. Most MHDUs are co-located with a Section 136 Place of Safety, are able to share staff and in some cases, have variable capacity through using flexible partitioning between units. MDHUs have the option of overnight stay – although this often takes the form of reclining seating rather than beds – with maximum length of stay restricted to, typically, 48 or 72 hours (Table 2). Overnight accommodation is single sex, again with flexible partitioning to enable the unit to respond to different numbers of male and female service users. Units tend to be small (capacity of about 6) with staff: service user ratios of at least 1:2 to allow substantial time for detailed assessment, brief intervention and onward referral/ signposting. Brief intervention focussed approaches and so on. Onward referral can be to NHS or third sector services providing therapeutic, social or practical support around, for example, housing, welfare and benefits and so on. MHDUs are typically nurse-led units with

consulting input from psychiatry and other mental health professionals, usually from a co-located acute ward and/ or shared with a Section 136 suite.

MHDU	Max LoS	Accommodation	Capacity	Referral route
South West London	48 hrs	Recliners	5(7 including Section 136 beds)	A&E (liaison), CRHT, Street Triage
Lincolnshire	24 hrs	Recliners	6	A&E (liaison), CRHT

Table 2: Key structural variation in MHDUs at site level

